Subjects may receive additional therapy with AU-011 at the maximum tolerated and feasible dose which is 3 repeat doses of $80~\mu g$ each followed by two laser applications (treatment regimen) as outlined in Section 8.3.3 of the protocol. Also, as outlined in Section 8.2.2 and the Injection and Laser Procedure Manual, if the fovea is near the tumor edge, an adjustment to the laser procedure should be performed on each treatment day.

Investigational product, dosage and mode of administration:

The investigational treatment is Light-activated AU-011, a combination product consisting of a drug (AU-011) and a laser (Aura Photoactivation System) that delivers 689 nm light to activate the drug once it is bound to the tumor cells. AU-011 drug substance is a modified human papillomavirus-derived, empty viral like particle (VLP) conjugated to approximately 200 molecules of a phthalocyanine-based photosensitizer IRDye®700DX (the "Dye").

AU-011 is administered by intravitreal injection. Laser light (689 nm) is applied to the CM from 6 hours to 8 hours after administration.

Statistical Methods:

Since this is an open-label, exploratory study, no formal hypothesis testing will be performed. Efficacy will be assessed at the Week 12, 26, 39, 52, 78 and 104 visits for any potential tumor response and changes in ETDRS best corrected visual acuity (BCVA). This will include change from baseline at each visit in tumor thickness by ultrasound and largest basal diameter by digital fundus photography. The proportion of subjects who meet the definition of stable disease (do not meet the definition of disease progression) will also be reported for each visit using change in tumor thickness and changes in largest basal diameter. Change from baseline in ETDRS BCVA letter score at Week 12 and at each subsequent visit and the proportion of subjects who lose or gain 5, 10 or 15 letters will also be evaluated.

Exploratory analyses will be performed for change in internal reflectivity of tumors by A-scan ultrasound at each visit and macular changes (foveal avascular zone and capillary density) by OCTA at each visit.

Background and demographic characteristics will be presented. Continuous variables will be summarized by descriptive statistics (sample size, mean, standard deviation, median, minimum and maximum). Discrete variables will be summarized by frequencies and percentages.

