6. INVESTIGATIONAL PLAN

6.1. Overall Study Design

Study Design:

This is an open-label, ascending single and repeat dose and cycle, multicenter study, designed to evaluate the safety, immunogenicity and efficacy of Light-activated AU-011 at 3 dose levels and single and 2 repeat dose regimens and cycles of Light-activated AU-011 and up to two laser applications in approximately 60 subjects with primary CM. The dose escalation design is shown in the figure below. Safety assessments will take place at all study visits and the efficacy assessments will commence at the Week 12 visit.

Figure 2 Dose Escalation Schematic

^{*}Alternating enrollment; enrollment in Cohorts 10 and 11 closed following approval of protocol revision 11 (Rev-11) at each site and subjects will be enrolled in Cohort 12.

Single Ascending Dose (SAD) Cohorts

Three subjects will receive a single IVT injection of Light-activated AU-011 low dose (20 μ g in 50 μ L). The injection is followed 6 to 8 hours later by exposure to 689 nm laser light. No more than one subject may be treated per day, and the treated subject must complete his/her 24-hour post-treatment visit with no safety issues before the next subject in a given cohort may be treated.

If all 3 subjects in the low dose group complete treatment without any dose limiting toxicity (DLT), escalation to the medium dose level (40 μ g in μ L) group will be initiated. If a DLT is observed in 1 subject in the low dose group, this group will be expanded to 6 subjects. Dose escalation will not be allowed if 2 or more subjects in the low dose group experience a treatment-related DLT. Instead, if 2 or more subjects in the low dose group experience a treatment-related DLT, dose reduction to 10 μ g in μ L may be considered for enrolling an additional 3 subjects.

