One week after the last subject in the low dose group completes treatment, the study medical monitor and independent ocular oncologist will review safety data for all subjects in the low dose group. After review and confirmation that the data support proceeding to treatment with the medium dose group, three subjects will receive a single IVT injection of Light-activated AU-011 medium dose (40 µg in µL). The injection is followed 6 to 8 hours later by exposure to 689 nm laser light. If all 3 subjects in the medium dose group complete treatment without any dose limiting toxicity (DLT), escalation to the high dose level group will be initiated. If a DLT is observed in 1 subject in the medium dose group, this group will be expanded to 6 subjects. If 2 or more subjects in the medium dose group experience a DLT after their treatment, this will confirm that the low dose level is the maximum feasible dose (due to formulation limits).

One week after the last subject in the medium dose group completes treatment, the study medical monitor and an independent ocular oncologist will review safety data for all subjects in the medium dose group. After review and confirmation that the data support proceeding to treatment with the high dose group, three subjects will receive a single dose of Light-activated AU-011 high dose (80 µg administered as 2 injections of 40 µg in µL not more than two hours apart). The second injection is followed 6 to 8 hours later by exposure to 689 nm laser light. If a DLT is observed in 1 subject in the high dose group, this group will be expanded to 6 subjects. If 2 or more subjects in the high dose group experience a DLT after their treatment, this will confirm that the medium dose level is the maximum feasible dose and the dose chosen for the repeat dose phase of the study will drop to one dose below the maximum feasible dose of 40 µg and the lower dose of 20 µg will be given as repeat doses.

Multiple Ascending Dose (MAD) Cohorts

One day after the last subject in the high dose group completes treatment, the study medical monitor and independent ocular oncologist will review safety data for all subjects and recommend proceeding to the repeat dose phase of the study.

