After review and confirmation that the data support proceeding to repeat dose regimens, 3 subjects will receive an intravitreal injection of 40 µg in µL of Light-activated AU-011 as 2 repeat doses 1 week apart. Each injection is followed 6 to 8 hours later by exposure to 689 nm laser light.

If all 3 subjects in this 2 repeat 40 µg dose group complete treatment without any dose limiting toxicity (DLT) after 2 injections, then this regimen may be investigated further in subsequent studies. If a DLT is observed in 1 subject in this 2 repeat 40 µg dose group, this group will be expanded to 6 subjects. If 2 or more subjects in this 2 repeat 40 µg dose group experience a DLT after their treatment, this will confirm that a lower repeat dose regimen should be investigated.

One day after the last subject in the 2 repeat 40 µg dose group completes treatment, the study medical monitor and independent ocular oncologist will review safety data for all subjects and identify whether it is safe to evaluate 3 repeat 40 µg doses in the next cohort of the study.

After review and confirmation that the data support proceeding to 3 repeat 40 µg dose regimen, 3 subjects will receive an intravitreal injection of 40 µg in µL of Light-activated AU-011 as 3 repeat doses 1 week apart. Each injection is followed 6 to 8 hours later by exposure to 689 nm laser light.

If all 3 subjects in this 3 repeat 40 µg dose group complete treatment without any dose limiting toxicity (DLT) after 3 injections, escalation to the next dose cohort will be initiated. If 2 or more subjects in this 3 repeat 40 µg dose group experience a DLT after their treatment, this will confirm that a fewer number of repeat administrations, or a lower dose at each administration should be investigated.

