One day after the last subject in the 3 repeat 40 μg dose group completes treatment, the study medical monitor and independent ocular oncologist will review safety data for all subjects and identify the maximum feasible dose for continued evaluation in the repeat dose phase of the study. After review and confirmation that the data support proceeding, an 80 μg single dose repeat laser regimen will be initiated. Three subjects will receive intravitreal administration of 80 μg of Light-activated AU-011 administered as 2 injections of 40 μg in μL (not more than 2 hours apart) followed by two 689 nm laser applications 30 minutes (\pm 10 minutes) apart, with the first of the 2 laser applications occurring 6 to 8 hours after the second injection.

If all 3 subjects in this 80 μ g single dose followed by 2 laser applications dose group complete treatment without any dose limiting toxicity (DLT), then the study may progress to the next cohort. If a DLT is observed in 1 subject in this 2 repeat laser applications following 80 μ g single dose group, this group will be expanded to 6 subjects. If 2 or more subjects in this 2 repeat laser applications following 80 μ g single dose group experience a DLT after their treatment, this will confirm that a lower dose followed by repeat laser regimen, or a repeat dose followed by single laser application, should be investigated further.

One day after the last subject in the 2 repeat laser applications following 80 µg single dose group completes treatment, the study medical monitor and independent ocular oncologist will review safety data for all subjects and identify whether it is safe to evaluate repeat laser applications after each of 3 repeat doses of 80 µg in the study.

After review and confirmation that the data support proceeding to the 3 repeat 80 µg dose regimen followed by a single laser application, 3 subjects will receive an intravitreal administration of 80 µg of Light-activated AU-011 administered as 2 injections of 40 µg in µL (not more than 2 hours apart) as 3 repeat doses one week apart. Each administration is followed 6 to 8 hours (after the second injection) later by exposure to 689 nm laser light.

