One day after the last subject in the 3 repeat $80 \mu g$ dose group, followed by a single laser application, completes treatment and 4 weeks after the last subject in the $80 \mu g$ single dose followed by 2 laser applications dose group complete treatment, the study medical monitor and independent ocular oncologist will review safety data for all subjects and identify whether it is safe to evaluate 3 repeat doses of $80 \mu g$, each followed by 2 repeat laser applications, in the next cohort of the study.

After review and confirmation that the data support proceeding to repeat laser applications after each of 3 repeat 80 µg doses, 3 subjects will receive an intravitreal administration of 80 µg of Light-activated AU-011 administered as 2 injections of 40 µg in µL (not more than 2 hours apart) as 3 repeat doses one week apart. Each administration is followed 6 to 8 hours (after the second injection) later by 2 exposures to 689 nm laser light 30 minutes (± 10 minutes) apart.

If all 3 subjects in this group, who receive 3 repeat 80 µg doses, each followed by 2 repeat laser applications, complete treatment and have been followed for 4 weeks without any dose limiting toxicity (DLT) after 3 weekly administrations, then this dose and regimen will be considered the

maximum feasible dose and investigated in the expanded cohort. If a DLT is observed in 1 subject in this 3 repeat $80~\mu g$ dose with 2 repeat laser applications group, this group will be expanded to 6 subjects. If 2 or more subjects in this 3 repeat $80~\mu g$ dose with 2 repeat laser applications group experience a DLT after their treatment, this will confirm that a fewer number of repeat administrations of either Light-activated AU-011 or laser, or both, or a lower dose of Light-activated AU-011 at each administration should be investigated further.

Four weeks after the final treatment of the final subject in this cohort, a review of the safety data (including EDI-OCT) by the study medical monitor and independent ocular oncologist will occur. If safety is confirmed, the 3 repeat 80 μ g dose with 2 repeat laser applications will be considered the maximum feasible and tolerated dose and this regimen will be expanded by up to 12 additional subjects in Cohort 9.

Repeat Cycle and Observation Cohorts

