The intention is to alternate the enrolment of Cohorts 10 and 11. If during the enrollment of these subjects, a subject has just been enrolled into Cohort 11 and a subject with documented growth presents, then that subject may instead be enrolled into Cohort 11 rather than Cohort 10 for which they would not be eligible due to the presence of documented growth and instead will be assigned to receive the first of 2 cycles of AU-011.

If 2 subjects experience a DLT during treatment with Cycle 2, as defined in Section 8.4.1., then no further subjects will receive Cycle 2 of AU-011 until discussed with the independent ocular oncologist and medical monitor and continuation of enrollment is confirmed.

Subjects with Documented Growth

Enrollment in Cohorts 10 and 11 was closed following approval of protocol revision 11 (Rev-11) at each site. An additional cohort, Cohort 12, of subjects with minimum defined levels of documented growth will be initiated to allow assessment of safety and efficacy of 2 cycles of AU-011 treatment in this key subgroup of subjects with CM. Since Cohort 12 has the same dose as Cohort 11 no safety review will be required.

Up to 15 subjects, who meet the criteria for a clinical diagnosis of CM with documented growth as defined in Inclusion Criteria 5C, will enter Cohort 12 and receive two cycles of AU-011 treatment (each cycle will be comprised of 3 repeat 80 µg doses, each followed by 2 repeat laser applications). Cycle 2 of AU-011 will be administered as 3 repeat 80 µg doses, each followed by 2 repeat laser applications no earlier than the Week 12 Visit and after resolution of any inflammation resulting from the first cycle or when the inflammation is minimal and decreasing based on investigator judgement. Cycle 2 should be administered as soon as reasonably possible after inflammation has resolved or is minimal and decreasing based on investigator judgement. If the fovea is near the tumor edge, an adjustment to the laser procedure should be performed on each treatment day of both cycles as outlined in section 8.2.2 and the Injection and Laser Procedure Manual.

If 2 subjects experience a DLT during treatment with Cycle 2, as defined in Section 8.4.1., then no further subjects will receive Cycle 2 of AU-011 until discussed with the independent ocular oncologist and medical monitor and continuation of enrollment is confirmed.

Study Methods

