8.4.2. Dose Escalation / Termination

Dose escalation to the next higher dose level, repeat dose group, repeat laser application or repeat cycle will be implemented only if less than 2 subjects in the prior cohort complete the treatment without a DLT.

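### SAP 9.2 narrows the protocol's DLT definition to drug-related events without declaring the change; separately, protocol 8.4.2 states the escalation condition backwards

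*Protocol*

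**What the plan says.** **DLT definition.** Protocol 8.4.1 defines a DLT as a treatment-related event, where treatment means drug, laser or both, that is severe enough to limit escalation. Protocol 10.4 names DLT incidence, by that definition, beside AEs and SAEs as the basis for judging safety and tolerability. The Cycle 2 pause in protocol 6.1 relies on the same definition: "If 2 subjects experience a DLT during treatment with Cycle 2, as defined in Section 8.4.1., then no further subjects will receive Cycle 2".

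SAP 9.2 replaces treatment-related with drug-related, and directly below it plans the table of subjects with DLTs by cohort and overall. SAP 4.9, which lists changes from the protocol, mentions only the tumor response criteria. The SAP's version history mentions no DLT change either.

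**Escalation rule.** Protocol 8.4.2 says that escalation "will be implemented only if less than 2 subjects in the prior cohort complete the treatment without a DLT". Protocol 6.1 says the following for cohorts with 0 of 3 DLTs:
- Cohort 1: "If all 3 subjects in the low dose group complete treatment without any dose limiting toxicity (DLT), escalation to the medium dose level" is to be initiated.
- Cohort 2: "escalation to the high dose level group will be initiated".
- Cohort 5: "escalation to the next dose cohort will be initiated".
- Cohort 6: "then the study may progress to the next cohort".

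For the step from Cohort 7 to Cohort 8, 6.1 gives no DLT count. The medical monitor and the independent ocular oncologist "will review safety data for all subjects and identify whether it is safe to evaluate 3 repeat doses of" 80 µg, each with two laser applications.

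The synopsis already names the outcome of escalation, the "maximum tolerated and feasible dose which is 3 repeat doses of" 80 µg, each with two laser applications.

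**The concern.** Safety is the primary objective, and DLT incidence is one of three measures that protocol 10.4 names for it. It should be reported by the definition under which cohorts could be expanded and Cycle 2 paused. The laser is not incidental here: the number of laser applications was itself escalated (two per dose in Cohorts 6 and 8), so an event attributed to the laser alone is the kind that the DLT count must be able to hold.

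The 8.4.2 sentence is a secondary point. Taken literally, it forbids escalation after a clean cohort and does not forbid it after a toxic one. Anyone auditing the escalation against 8.4.2 would find that every step taken after a clean cohort departs from the text.

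**Working it through.** The plan states no operating characteristic or sample size calculation for DLTs, so there is no figure to reproduce. The check compares texts and enumerates the rule.

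**1. Does drug-related in SAP 9.2 include the laser?**
- SAP 9.3 reports events related to study drug, to injection procedure and to laser separately, and the AE listing carries a separate relationship for each. In the SAP's own safety terms, a laser-only event is not drug-related.
- SAP 3.2, on Cohort 1, speaks of a treatment-related DLT. The SAP is therefore not consistent with itself.
- SAP 9.2 is the only place where the SAP defines a DLT. SAP 3.2 and 4.5.2 repeat the Cycle 2 pause without the protocol's reference to 8.4.1.

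**2. Effect of one omitted laser-only DLT.** The change in reported incidence is 100/n percentage points, with n the planned or expanded cohort size:

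| n | Where it arises | Change |
|---|---|---|
| 3 | Escalation cohort | 100/3 = 33.3 |
| 6 | Expanded cohort; about the size of Cohorts 10 and 11 | 100/6 = 16.7 |
| 12 | Cohort 9 (maximum) | 100/12 = 8.3 |
| 15 | Cohort 12 (maximum) | 100/15 = 6.7 |

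A cohort expanded because of one laser-only DLT, with no other DLT, would show 0 of 6 (0%) instead of 1 of 6 (16.7%). The table would then not explain why the cohort was expanded.

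**3. Protocol 8.4.2 as written.** With n completers and k DLTs, the condition is n − k < 2. The evident intention is k < 2.

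| n | k | Without a DLT | 8.4.2 as written | Intended |
|---|---|---|---|---|
| 3 | 0 | 3 | blocked | permitted |
| 3 | 1 | 2 | blocked | permitted* |
| 3 | 2 | 1 | permitted | blocked |
| 3 | 3 | 0 | permitted | blocked |
| 6 | 0–1 | 6–5 | blocked | permitted |
| 6 | 2–4 | 4–2 | blocked | blocked |
| 6 | 5–6 | 1–0 | permitted | blocked |

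*Where the plan calls for expansion to 6 at 1 of 3, that still applies, because the condition is necessary and not sufficient.

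A cohort expanded after 1 of 3 can have at most 1 + 3 = 4 DLTs. If all complete, at least 6 − 4 = 2 are free of a DLT, so it can never satisfy 8.4.2 as written.

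**4. Comparison with protocol 6.1.** Cohorts 1 to 8 contain 7 escalation steps.
- At 0 of 3, 6.1 moves on after Cohorts 1, 2, 5 and 6, where 8.4.2 blocks. For Cohorts 3, 4 and 7 it ties no go-on clause to 0 of 3, so there is no explicit conflict.
- At 2 or more, 6.1 bans escalation for Cohort 1, where 8.4.2 as written permits it at 2 or 3 of 3. For Cohorts 2 to 6, 6.1 names a lower maximum, a lower dose or a less intensive regimen.
- After Cohort 7 no DLT-count rule is stated other than 8.4.2; there is only the safety review.
- The Cycle 2 pause counts subjects with a DLT, which confirms the intended direction.

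**The case against.** **On SAP 9.2.** SAP 4.5.1, under its description of study drug, presents a combination product, so drug-related might be meant to cover both parts. That section, however, itself names the drug and the laser as two components, and SAP 9.3 keeps their attributions apart. The objection does not rescue the wording.

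A better objection is that little would be lost. A laser-only ocular event in the study eye would still appear in the tables of events related to drug and/or laser, including those by worst severity. The AE listing carries a DLT flag. The SAP does not say whether the DLT table is built from that flag or from the 9.2 definition. All of this stands and limits the point to one table and one listing. The Cycle 2 pause runs under the protocol, which cites 8.4.1, so the SAP wording changes no treatment decision.

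**On 8.4.2.** It is almost certainly a drafting slip. The synopsis, 6.1 and SAP 3.2 give the sensible direction, each step required review by the medical monitor and an independent ocular oncologist, and escalation is over. This stands too.

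**Stronger readings that the documents do not support.** A reader might infer that DLTs were missed, but no laser-only DLT is reported. A reader might infer that subjects were escalated unsafely, but nothing shows that 8.4.2 was followed literally. A reader might infer that only Cohort 1 had a rule at 2 or more DLTs, but Cohorts 2 to 6 have stated consequences as well. A reader might infer that no DLT data exist for Cohort 7, but SAP 9.2 tabulates DLTs for every cohort; only a second decision rule is absent.

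**Conclusion.** Both texts are wrong as written. The SAP 9.2 definition is the main point: an undeclared departure from the protocol on a named measure for the primary objective. Its effect is conditional. It needs a DLT attributed to the laser alone, and a table built from the 9.2 wording rather than from the flag. If both hold, each such event lowers a cohort's reported incidence by 6.7 to 33.3 points for n between 15 and 3.

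The inversion in 8.4.2 is secondary. It contradicts 6.1 at 0 of 3 for Cohorts 1, 2, 5 and 6, and at 2 or more for Cohort 1. No further subject is exposed through it, because escalation is complete. It matters for the record, most of all at the step from Cohort 7 to Cohort 8, where it is the only DLT-count rule stated.

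**What to change.** 1. In SAP 9.2, use the protocol 8.4.1 definition (drug, laser or both). Check Table 14.3.1.3 and Listing 16.3.2 against the DLT flag in the AE listing, and re-run them if they differ. The cost is one phrase and one check. No new data are needed, since the listing already holds the flag and the separate relationships. SAP v5.0 already follows the first database lock, so the change should be dated and its reason given.

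2. State in the study report that the escalation condition is: only if fewer than 2 subjects in the prior cohort experience a DLT. Report which rule was applied at each of the 7 steps, including Cohort 7 to Cohort 8. Do not add an expansion rule for Cohort 7, because neither document contains one. A protocol amendment for this alone is not worth the IRB submission that section 14.3 calls for; correct 8.4.2 only if the protocol is amended for another reason. The cost is a short note.
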